## **11.2 Planned Statistical methods of analysis**

Continuous variables will be presented as means and standard deviations, while categorical variables will be reported as frequencies and percentages. Independent sample t-tests will be used to compare continuous variables between groups, and Pearson's chi-square test will be used for comparisons of categorical variables. One-way analysis of variance (ANOVA) will be applied to assess differences among the multiple subgroups. All statistical analyses will be conducted using SPSS (Statistical Package for the Social Sciences). A p-value of less than 0.05 will be considered indicative of statistical significance.

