# 4. Study Design

## 4.1 Overall Design

The study employs a novel non-powered bi-manual rehabilitation device based on mechanical transmission principles, specifically designed for upper limb training in post-stroke

patients. The device operates through a linear guide rail system that enables the unaffected limb to drive the movement of the affected limb along a mirrored trajectory. This bilateral training approach allows simultaneous motion of both upper limbs, enabling the unaffected side to assist in generating active movement in the hemiplegic arm.

Key features of the device include: (1) bilateral limb synchronization, whereby movement of the unaffected upper limb facilitates motion of the affected limb; (2) a purely mechanical, power-free transmission system utilizing linear rail sliders; and (3) training guided along specific two-dimensional movement trajectories. The device is expected to maintain or improve joint range of motion (ROM), reduce spasticity as measured by the Modified Ashworth Scale (MAS), and promote neuroplasticity in the affected neural pathways.

The structural design centers around a central transmission module that links the motion of the two limbs via linear rails to minimize mechanical resistance. The forearm is secured using an end-effector mechanism, and the device allows for directional movement through longitudinal and lateral rail systems. Different training trajectories can be achieved by varying the patient's seated position, supporting functional training across a range of upper limb motion patterns.

Prior to training, the rehabilitation physician evaluates the affected shoulder and elbow joints using the Brunnstrom Recovery Stage, Fugl-Meyer Assessment for Upper Extremities (FMA-UE), and MAS. Based on MAS scores, patients are stratified into two groups: those with MAS <1 and those with MAS  $\geq$ 1. Participants are then randomly assigned to either the experimental group—receiving bilateral upper limb training with the device combined with conventional occupational therapy—or the control group—receiving only conventional upper limb occupational therapy.

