For the experimental group, patients are instructed on how to use the device, and a therapist provides assistance during operation. After the initial session, patients repeat the same training one week later to assess test-retest reliability. Training includes two components: (1) single-joint exercises targeting either the shoulder or elbow, with 20 repetitions per joint for 5 sets, each set separated by a 30-second rest; and (2) dual-joint exercises involving functional movement along rectangular and triangular paths, also conducted in 5 sets of 20 repetitions with similar rest intervals.

Control group training involves conventional functional tasks targeting the affected limb, such as box-pushing (standing or seated), alternating push-pull activities, and use of a hand-cycle. Both groups train for 30 minutes per day, five days a week, for a total of 15 sessions over three weeks. All participants continue their routine rehabilitation treatments throughout the study. At the conclusion of the three-week intervention, the rehabilitation physician reassesses Brunnstrom stage, FMA-UE, and MAS to evaluate functional changes in the affected upper limb.

To assess usability and user satisfaction, both patients and therapists complete the System Usability Scale (SUS) and a satisfaction questionnaire following the training period. The SUS consists of 10 items rated on a five-point Likert scale ranging from "strongly disagree" to "strongly agree." Odd-numbered items are positively worded, while even-numbered items are negatively worded. Scoring involves subtracting 1 from positive item scores and subtracting the original score from 5 for negative items; the total is then multiplied by 2.5 to yield a final SUS score out of 100.

The satisfaction questionnaire assesses five domains—overall satisfaction, comfort, ease of donning the device, perceived improvement in ROM, and rehabilitative assistance—using a

five-point Likert-type scale ranging from 1 (very poor) to 5 (very good).

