# 11. Statistical Considerations

## **11.1 Sample size Determination**

Based on the recommendations by Lewis and Sauro (2009), a minimum of 12 participants per group is considered appropriate for usability testing. In this study, participants will be categorized into four subgroups based on muscle tone classification (MAS < 1 or MAS  $\geq$  1) and treatment allocation (experimental or control group), resulting in a minimum required sample size of 48 (12 participants per subgroup). To account for an anticipated dropout rate of approximately 25%, an additional 12 participants will be recruited, leading to a total target enrollment of 60 stroke patients. In addition, 10 trained healthy participants—including caregivers or family members—will be included for usability assessments and device operation training. The total number of evaluable subjects for the study will therefore be 70.

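### The planned t-tests and one-way ANOVA ignore baseline FMA-UE, the t-tests also ignore the MAS stratum, and the ANOVA cannot isolate the device effect

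*Combined protocol and SAP*

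**What the plan says.** Section 11.2 gives the whole analysis plan: "Independent sample t-tests will be used to compare continuous variables between groups", "Pearson's chi-square test will be used for comparisons of categorical variables", and "One-way analysis of variance (ANOVA) will be applied to assess differences among the multiple subgroups". The synopsis repeats these methods. Section 11.2.1 lists FMA-UE as the primary endpoint without a model, and section 11.2.3 (additional analysis) is marked not applicable.

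On the subgroups, section 11.1 says that "participants will be categorized into four subgroups based on muscle tone classification" and by treatment allocation. It sets 12 per subgroup, 48 in all, raised to 60 for dropout.

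On design, section 4.1 has FMA-UE and MAS assessed before training, then says "Based on MAS scores, patients are stratified into two groups" (below 1, and 1 or above), after which "Participants are then randomly assigned to either the experimental group" or to the control group. After three weeks "the rehabilitation physician reassesses Brunnstrom stage, FMA-UE, and MAS to evaluate functional changes in the affected upper limb". The schedule in section 4.3 confirms FMA-UE and MAS at both assessments.

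**The concern.** There are three linked gaps.

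- **Unused information.** Baseline FMA-UE and the MAS stratum are known before treatment, and baseline FMA-UE is likely to predict the 3-week score. The two-arm test uses neither explicitly. With about 24 completers per arm, that precision matters for the primary endpoint.
- **Undefined analysis variable.** The plan does not say whether the t-test is run on 3-week scores or on changes. The reference to functional changes in section 4.1 hints at changes but does not define the variable, so the choice is open after the data are seen.
- **A subgroup test that does not address the device.** A one-way ANOVA over four MAS-by-arm cells asks whether all four means are equal. Patients with higher and lower spasticity may differ whatever the treatment, so a significant result would not show that the device works, and no contrast is planned to separate the two.

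**Working it through.** **Inputs from the documents.** Four cells of 12 give 4 × 12 = 48, or 24 per arm; 48 × 1.25 = 60 reproduces the enrolment target. The significance level is 0.05, taken as two-sided because sidedness is not stated. The sample size follows a usability rule, so there is no stated power to reproduce.

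**Assumptions, not in the documents.** Baseline-to-final correlation r = 0.5, 0.7, 0.9; equal SD at both times; device effect 0.5 SD of the 3-week score; stratum differences as listed below.

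**1. Two-arm comparison.** The residual SD relative to the 3-week score is 1 for the score itself, √(2(1−r)) for change, and √(1−r²) for ANCOVA. The noncentrality for a 0.5 SD effect is (24/2) × 0.5² / residual variance = 3 / residual variance. Error df are 46, 46 and 44. The 95% CI half-width is t(0.975) × √(2/24) × residual SD.

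| | r = 0.5 | r = 0.7 | r = 0.9 |
|---|---|---|---|
| Power, 3-week score | 40% | 40% | 40% |
| Power, change | 40% | 59% | 97% |
| Power, ANCOVA | 50% | 66% | 97% |
| Half-width, 3-week score (SD) | 0.58 | 0.58 | 0.58 |
| Half-width, change (SD) | 0.58 | 0.45 | 0.26 |
| Half-width, ANCOVA (SD) | 0.50 | 0.42 | 0.25 |

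The worked case r = 0.7: the ANCOVA residual variance is 1 − 0.49 = 0.51, the noncentrality is 3/0.51 = 5.88, and the half-width is 2.015 × 0.289 × 0.714 = 0.42 SD.

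The formula treats the baseline slope as known. Simulation of 10,000 trials with the slope estimated and the stratum fitted gives ANCOVA power of 48.6%, 64.9% and 96.9%, one to two points lower at r = 0.5 and 0.7.

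**2. Ignoring the stratum in the t-test.** In simulation with no device effect and stratum differences of 0.5 and 1 SD, the t-test's true size is about 4.3% and 2.8% if arms are balanced within strata. With simple randomisation it is about 5% in both cases. Section 4.1 does not say how balance within strata is achieved.

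**3. Four-cell ANOVA with no device effect.** For a stratum difference s (in SD of the analysed score), the noncentrality is 48 × (s/2)², with 3 and 44 df.

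| s | Noncentrality | Probability of a significant F |
|---|---|---|
| 0.2 | 0.48 | 8% |
| 0.3 | 1.08 | 11% |
| 0.5 | 3.00 | 25% |
| 1.0 | 12.00 | 80% |

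The test keeps its 5% level for the hypothesis that all four means are equal. These figures show only that significance says little about the device. If changes are analysed, s is a difference in mean change between strata.

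**4. ANOVA power for the device.** With a 0.5 SD device effect in both strata and no stratum effect, the noncentrality is 3. The 3-df test has 25% power, against 40% for a 1-df arm comparison.

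**5. Device effect within one stratum (12 v 12).** The half-width is t(0.975) × √(2/12) × residual SD: 0.82 SD unadjusted (44 df), and 0.71, 0.59 and 0.36 SD with ANCOVA (43 df) at r = 0.5, 0.7 and 0.9.

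**The case against.** The strongest reply is that the two-arm t-test already estimates the device effect without bias, and that if it is run on changes, as section 4.1 hints, most of the gain has already been taken. That is largely right. Against a change-score test, ANCOVA adds 10, 7 and under 1 point of power by formula, or about 9, 6 and 0.3 points by simulation. At a correlation of 0.95 the gain disappears. The larger gains of 10, 26 and 58 points apply only against a 3-week-score test. But the plan does not commit to changes, and over the range examined ANCOVA is never worse.

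It may also be said that section 11.2 never names the four cells and never claims that a significant F shows a device effect. The four-cell reading is an inference, but those are the only subgroups the document defines, in the section immediately before. The fair conclusion is that the ANOVA is uninformative about the device, not that it undermines the arm comparison.

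Two further points stand as limits. The synopsis and section 4.2 bring 60 retrospective patients into the analysis without placing them in any model; everything here concerns the randomised patients. And 25% dropout from 60 leaves 60 × 0.75 = 45, not 48, which would lower precision slightly for every method.

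**Conclusion.** The concern holds. No covariate, stratum term, factorial model or contrast appears anywhere in the plan, although both covariates are collected before treatment. For the t-test the fault is lost precision, not false positives. The loss is modest if changes are analysed and substantial if 3-week scores are, and the plan leaves that open. For the ANOVA the fault is one of interpretation: as planned, it cannot tell a device effect from a spasticity effect. That conclusion does not depend on the correlation, though the size of the problem depends on how far the strata differ. All sizes rest on assumed correlations, effect and stratum differences, which the documents do not give. The change should be made, but its absence does not invalidate the arm comparison.

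**What to change.** In sections 11.2 and 11.2.1, and in the synopsis, name the primary analysis as an ANCOVA of 3-week FMA-UE on arm, baseline FMA-UE and MAS stratum, in the randomised patients, reporting the adjusted mean difference with its 95% CI. This also settles which score is analysed. Replace the one-way ANOVA with the same model plus an arm-by-stratum interaction, and show the device effect with its 95% CI in each stratum, labelled supportive in view of the width of the within-stratum intervals.

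State in the SAP how the stratum is derived. Section 4.1 assesses both shoulder and elbow and does not say which MAS score sets it; the model should use the stratum applied at randomisation.

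The cost is SAP wording only. No patients, visits or measurements are added, SPSS fits the model, and with 48 completers the primary analysis has 44 error degrees of freedom instead of 46.

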#### **3.2.2 Secondary endpoints:**

Brunnstrom stage

Spasticity: Modified Ashworth Scale (MAS)

Usability: System Usability Scale (SUS)

Test-retest reliability of repeated training sessions

User satisfaction: Satisfaction questionnaire

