# 5. Study Population

#### 5.1 Inclusion Criteria

- Stroke onset  $\leq 12$  months
- Age 18–70 years
- Stable physiological and neurological status for  $\geq$ 72 hours
- Able to follow at least two-step commands
- Written informed consent obtained
- Unilateral upper limb hemiplegia
- Brunnstrom stage > I (proximal UE)
- MAS < 3 (affected UE)

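### No test is assigned to MAS or Brunnstrom stage, and no listed test both respects their order and uses the baseline grade; power falls clearly if chi-square is the one used

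*Combined protocol and SAP*

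**What the plan says.** Sections 3.2.2, 7 and 11.2.1 list Brunnstrom stage and MAS as secondary endpoints. Both are graded before treatment, and section 4.1 says that after the three weeks "the rehabilitation physician reassesses Brunnstrom stage, FMA-UE, and MAS"; the schedule in section 4.3 agrees.

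The protocol itself uses both scales as ordered. Eligibility (section 5.1) requires a Brunnstrom stage above I and a MAS below 3, and patients are stratified at MAS below 1 versus 1 or more (section 4.1).

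Section 11.2 gives the whole inferential toolkit:
- The rule for data treated as continuous: "Independent sample t-tests will be used to compare continuous variables between groups"
- The rule for data treated as categorical: "Pearson's chi-square test will be used for comparisons of categorical variables"
- The rule where more than two sets of patients are compared: "One-way analysis of variance (ANOVA) will be applied to assess differences among the multiple subgroups"

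The synopsis names the same three tests. Section 11.2.1 repeats the endpoint list without attaching a test to any item, and section 11.2.3 plans no additional analysis. No rank, trend or ordinal-regression method appears anywhere. The plan does not say whether MAS or Brunnstrom stage counts as continuous or categorical, or whether the post-treatment grade or its change from baseline is compared.

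**The concern.** The plan sorts variables into continuous and categorical, and an ordered grade fits neither heading well. Two routes are therefore open, and the choice could be made after the data are seen.

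- **Categorical route.** Chi-square gives the same answer if the grades are shuffled. A consistent shift of patients towards better grades is tested against every possible pattern of difference, which dilutes power.
- **Continuous route.** A t-test or ANOVA on the grade numbers keeps the order. It treats every step as the same size and reports a mean difference in grades, which is hard to interpret.

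As listed, neither route adjusts for the baseline grade, although it is collected on every patient and is likely to predict the final grade. Section 4.1 expects the device to reduce spasticity as measured by MAS, so this is a stated device claim and worth testing well.

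**Working it through.** **1. Patients per arm.** Section 11.1 takes four subgroups of 12: 4 × 12 = 48. Adding 25% gives 48 × 1.25 = 60, which reproduces the stated enrolment. With 1:1 allocation (assumed; no ratio is stated) that is 24 to 30 per arm. The plan states no power for MAS or Brunnstrom stage, so there is no power figure to reproduce.

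**2. Assumptions.** The documents give no effect size, number of grades or distribution of grades. Assumed: two-sided 0.05; 4 to 6 categories; a common odds ratio (OR) of 2 to 4 under proportional odds. If c_j is the control arm's cumulative share up to grade j, the other arm's is c'_j = o_j/(1 + o_j), with o_j = OR × c_j/(1 − c_j).

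**3. Simulated power.** 20,000 trials per row. Chi-square has (observed categories − 1) df, the rank test is Wilcoxon-Mann-Whitney corrected for ties, and the t-test uses integer scores. No test uses baseline.

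| Categories | Per arm | OR | Chi-square | Rank | t-test | Rank − chi-square |
|---|---|---|---|---|---|---|
| 4, even | 24 | 3 | 0.366 | 0.537 | 0.537 | 0.171 |
| 5, even | 24 | 3 | 0.328 | 0.551 | 0.550 | 0.223 |
| 6, even | 24 | 3 | 0.295 | 0.560 | 0.562 | 0.265 |
| 4, even | 30 | 3 | 0.457 | 0.634 | 0.631 | 0.177 |
| 6, even | 30 | 3 | 0.370 | 0.651 | 0.649 | 0.281 |
| 4, even | 30 | 4 | 0.660 | 0.819 | 0.816 | 0.159 |
| 6, skewed | 24 | 4 | 0.406 | 0.710 | 0.668 | 0.304 |
| 6, skewed | 30 | 4 | 0.526 | 0.815 | 0.769 | 0.289 |

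Skewed shares are .30/.25/.20/.10/.10/.05. Over all runs with 4 to 6 categories and OR 3 or 4, the chi-square deficit runs from 0.159 to 0.304. At OR 2, chi-square has 0.12 to 0.20 and the rank test 0.25 to 0.32. With only three even categories, 24 per arm and OR 3, the deficit is about 0.10 (0.416 versus 0.516).

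The t-test stays close to the rank test. The largest gap is 0.815 − 0.769 = 0.046.

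**4. Analytic cross-check.** For 80% power at 0.05, the noncentrality needed is 7.849 with 1 df and 10.90, 11.94 and 12.83 with 3, 4 and 5 df (4, 5 and 6 categories). The sample-size ratios are 10.90/7.849 = 1.39, 11.94/7.849 = 1.52 and 12.83/7.849 = 1.63. Held at 7.849, power falls from 80% to 64%, 60% and 56%. This assumes that the whole effect lies along the ordered direction.

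**5. Chi-square under no effect.** With 4 to 6 categories, rejection was 0.037 to 0.052. With 24 per arm, 70% to 100% of the simulated tables had an expected count below 5.

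**6. Value of the baseline grade.** A further simulation used 24 per arm, OR about 3, four assumed categories and an assumed baseline-to-final correlation of 0.5 to 0.85. Power was 25–29% for chi-square, 44–47% for the t-test on the post-treatment grade and 55–80% for ordinal regression adjusted for baseline. With no effect, the regression rejected in 5–7% of 600 runs. The simulation error there is √(0.05 × 0.95/600) = 0.009, so a slight excess over 5% cannot be excluded.

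**The case against.** The strongest reply is that the plan never sends these scales to chi-square. That is right. A reader might infer from section 11.2 that graded scales are categorical and so go to chi-square, but the documents classify neither scale. The power loss is therefore conditional on that choice.

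Two other stronger readings also fail:
- **Every listed test loses power.** A reader might infer this because none is an ordinal method. Against an unadjusted rank test, the t-test gives up at most about 5 points and usually nothing. What remains against it is the equal-step assumption and the unused baseline.
- **Sparse cells make the chi-square p-value unreliable.** Low expected counts are common at this size, but simulated type I error is at or slightly below nominal. A rule of thumb is broken without material harm.

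It can also be said that a t-test on change scores would use the baseline. It would, but the plan does not define either endpoint as a change, and differences of grades lean still harder on equal steps.

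Finally, the sizes rest on assumed odds ratios and shares, and even a rank test has only 50–65% power at an odds ratio of 3. Both remarks stand. The direction of the chi-square loss held in every scenario with an effect, but a better test does not make these endpoints well powered.

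**Conclusion.** The point holds in conditional form. Sections 11.2 and 11.2.1 leave MAS and Brunnstrom stage without an assigned test, and no listed test, as described, both respects the order and uses the baseline grade. If chi-square is used, about 16 to 30 points of power are lost against a rank test. If a t-test is used, unadjusted power is about the same as a rank test's. The avoidable costs are then the equal-step assumption and the precision that baseline adjustment would bring.

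The figures depend on the assumed odds ratio, number and spread of categories, 1:1 allocation, two-sided testing and, for the adjusted model, the baseline-to-final correlation. Direction and rough size are dependable; single values are not. Both endpoints are secondary, so the primary FMA-UE comparison is untouched.

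**What to change.** In section 11.2.1, name one analysis for each of the two scales:

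- **MAS:** proportional-odds ordinal regression of the post-treatment grade on arm and baseline MAS entered as a score. Leave the MAS stratum out, because baseline MAS already determines it.
- **Brunnstrom stage:** the same model on arm, baseline stage entered as a score, and MAS stratum.
- **Both:** report the common odds ratio with its 95% confidence interval, and test the arm effect with a likelihood-ratio test.
- **Fallback:** if the model is unstable at about 48 patients, use a rank test stratified by MAS stratum. State in advance what counts as unstable.
- **Chi-square:** keep it for nominal variables.

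The cost is SAP wording; SPSS, the planned software, has ordinal regression, and no extra patients, visits or measurements are needed. The downside is reliance on the proportional-odds assumption and on fitting a model in a small sample, so this is a cheap improvement, not a free one.

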#### 11.2.1 Efficacy analysis

#### Primary endpoint:

- Fugl-Meyer Assessment for Upper Extremities (FMA-UE)
- Secondary endpoints:
  - Brunnstrom stage
  - Spasticity: Modified Ashworth Scale (MAS)
  - Usability: System Usability Scale (SUS)
  - Test-retest reliability of repeated training sessions
  - User satisfaction: Satisfaction questionnaire

#### 11.2.2 Safety analysis

Not Applicable

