# 1. Synopsis

Protocol Title : Usability Analysis of a Novel Bilateral Upper Limb Rehabilitation Device in Post-Stroke Hemiplegia
Study Objectives :
Post-stroke patients commonly experience upper limb impairment, with approximately 85% affected during the acute phase and 40% continuing to experience dysfunction in the chronic phase. Functional upper limb use is essential for daily living and social participation. However, current rehabilitation often requires external assistance or costly robotic devices, which limits accessibility. This study proposes a novel, non-powered mechanical bilateral upper limb rehabilitation system that is easy to don and operate, reduces assistance needs, and allows patients to independently perform rehabilitation exercises. The device aims to improve treatment
accessibility and efficiency while promoting upper limb recovery. The study consists of three
phases: Prototype adjustment; Device fitting and training assessment; Usability and satisfaction evaluation.
Investigational product(s) :
A non-powered, mechanically structured bilateral rehabilitation device designed to facilitate independent upper limb training and enhance rehabilitation accessibility.
Development Phase : I III III IIV Other Not applicable
Study Design :

 
1. ■ Experimental Group : Bilateral upper limb training with the novel device + conventional occupational therapy
 
■ Control Group : □ Placebo
 
□ Study Drug (Name \ Dose \ Usage)
 
■ Other : Upper limb functional training + conventional occupational
 

therapy

 
2. Blinding : ■ Open □ Evaluator-blind □ Single-blind(patient) □ Double-blind(patient+PI)
 
□ Double Dummy □ Other
 
3. Randomization: ■ Yes □ No
 

$4 \blacksquare \text{Parallel design} \square \text{Crossover design} \square \text{Other} \square \text{Not applicable}$
4. Tratalier design Crossover design Conter Not applicable

 
6. Study Period: 1 years (2023/08/01-2024/07/31)
 

6. Dose adjustment : $\Box$ Mandatory $\Box$ Selectively $\Box$ No $\blacksquare$ Not applicable
7. Study location : Single Multi-center Global

 
Endpoints (Outcome measure) :
 
Primary endpoint:
 
Fugl-Meyer Assessment for Upper Extremities (FMA-UE)
 
Secondary endpoint:
 
Brunnstrom stage
 

- Spasticity: Modified Ashworth Scale (MAS)
- Usability: System Usability Scale (SUS)
- Test-retest reliability of repeated training sessions

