#### 2.4 Risks / benefits Assessment

During the operation of the equipment, there may be friction and shear effects on the skin, leading to potential skin lesion. Therefore, before conducting rehabilitation programs with the Synslai device, the skin that will touch the device will be covered with a bandage to avoid possible skin damage. Furthermore, risks are held to a minimum due to anonymous coding and keeping all data confidential with no identification to specific participants. No undue stress or uneven medical managements is anticipated as a result of patient's participation. Benefits for the participants is to be able to receive more types and longer time period of post-stroke rehabilitation programs for upper limbs paralysis. It facilitates the functional recovery of post-stroke hemiplegia.

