## 9.1 Definitions and reports of Adverse Events

All adverse events that occur after the informed consent is signed (including run-in) must be recorded on the adverse event CRF (paper and/or electronic) whether or not related to study agent. AE Data Elements including:

- AE reported date
- AE Verbatim Term
- CTCAE Term (v 5.0)
- Event onset date and event ended date
- Severity grade
- Attribution to study agent (relatedness)
- Whether or not the event was reported as a Serious Adverse Event (SAE)
- Action taken with the study agent
- Outcome of the event
- Comments

Identify the adverse event using the NCI Common Terminology Criteria for Adverse Events (CTCAE) version 5.0. The CTCAE provides descriptive terminology and a grading scale for each adverse event listed.

AEs will be assessed according to the CTCAE grade associated with the AE term. AEs that do not have a corresponding CTCAE term will be assessed according to their impact on the participant's ability to perform daily activities as follows:

Grade	Severity	Description
1	Mild	Barely noticeable, does not influence functioning
		Causing no limitations of usual activities
2	Moderate	• Makes participant uncomfortable, influences functioning
		Causing some limitations of usual activities

3	Severe	
 
Severe discomfort, treatment needed
 
Severe and undesirable, causing inability to carry out usual activities
 

4	Life threatening	• Immediate risk of death
		Life threatening or disabling
5	Fatal	Causes death of the participant

The possibility that the adverse event is related to study drug will be classified as one of the following: not related, unlikely, possible, probable, definite.

**DEFINITION of Serious Adverse Events**: ICH Guideline E2A and GCP of Taiwan define serious adverse events as those events, occurring at any dose, which meet any of the following criteria:

- Results in death
- Is life threatening (Note: the term life-threatening refers to an event in which the patient was at risk of death at the time of the event; it does not refer to an event which hypothetically might have caused death if it were more severe).
- Requires inpatient hospitalization or prolongation of existing hospitalization
- Results in persistent or significant disability/incapacity
- Is a congenital abnormality/birth defect
- Events that may not meet these criteria, but which the investigator finds very unusual and/or potentially serious, will also be reported in the same manner.

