#### 9.2 Adverse event follow-up

All AEs, including lab abnormalities that in the opinion of the investigator are clinically significant, will be followed according to good medical practices and documented as such. Site staff should send follow-up reports as requested when additional information is available. Additional information should be entered on the IRB of Chang Gung Medical Foundation of SAE form in the appropriate format. Follow-up information should be sent to Chang Gung Medical Foundation IRB as soon as possible according to IRB's Serious Adverse Event Reporting Procedures and Guidelines.

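### Safety assessment and safety analysis are declared inapplicable although the plan names a device skin risk and records every adverse event, so no safety summary is pre-specified

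*Combined protocol and SAP*

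**What the plan says.** Section 11.2.2 consists of "Not Applicable", and Section 8 contains the same two words and nothing else. Both are printed section content, not redactions or gaps in extraction.

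Other sections treat safety as applicable:

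- Section 2.4 names a harm specific to the device: "there may be friction and shear effects on the skin, leading to potential skin lesion". It adds a precaution: "the skin that will touch the device will be covered with a bandage to avoid possible skin damage".
- Section 9.1 requires that "All adverse events that occur after the informed consent is signed (including run-in) must be recorded on the adverse event CRF", whether or not related. The listed data elements include the verbatim term, CTCAE v5.0 term, severity grade, attribution, SAE status and outcome. On grading it says "AEs will be assessed according to the CTCAE grade associated with the AE term".
- Section 9.2 says that AEs "will be followed according to good medical practices and documented as such".
- Section 9 sends SAEs to the IRB.

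On the state of knowledge about the device, Section 4.1 says "The study employs a novel non-powered bi-manual rehabilitation device", and the Synopsis lists the study "phases: Prototype adjustment; Device fitting and training assessment; Usability and satisfaction evaluation". Sections 2.2 (preclinical data) and 2.3 (clinical data) give no data.

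**The concern.** The plan identifies a possible harm and obliges the site to collect graded, attributed data that would capture it. It then states that neither assessment nor analysis of safety applies. An analyst who follows Section 11.2.2 would have no safety set, no table and no denominator. Whether harms appear in the trial report would be decided after the data are known.

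At stake is the balance of the conclusion. The trial could report that the device is usable and that patients are satisfied, with no planned estimate beside it of the one device harm the protocol names. If the report instead remarked informally that no lesions occurred, readers would have no interval to show how little a small arm can exclude.

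**Working it through.** **Does any other section supply a safety summary?**

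- Endpoints (Synopsis, 3.2, 7, 11.2.1): FMA-UE, Brunnstrom stage, MAS, SUS, test-retest reliability and satisfaction. There is no safety variable.
- Schedule (4.3): no AE row and no skin check.
- Analysis population (11.3): in substance restates eligibility. No safety set is defined.
- General methods (11.2): frequencies, percentages and chi-square tests for categorical variables. These could be applied to AEs, but 11.2.2, the specific subsection beneath, disclaims a safety analysis.
- SAE reporting (9): case-by-case reporting to the IRB. A non-serious skin lesion would not ordinarily go through it.
- Missing data (Synopsis, 11.4): incomplete cases are omitted. A patient who stopped because of a skin lesion and missed the post-treatment assessment would leave the planned analyses, and no safety table would record why.

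So no section restores a planned safety summary.

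**How informative would a summary be at this sample size?**

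The plan's own figure, from Section 11.1: 4 subgroups × 12 = 48, and 48 + 12 (25% of 48) = 60 stroke patients. This reproduces the stated 60.

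The allocation ratio is not stated. Assuming 1:1, 60 / 2 = 30 device patients, all of whom start training.

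- Exact two-sided 95% upper limit with 0 of n: 1 − 0.025^(1/n). For n = 30: 1 − 0.025^(1/30) = 0.116, or 11.6%.
- Sensitivity to the ratio: with 20 device patients (1:2), 1 − 0.025^(1/20) = 16.8%. With 40 (2:1), 1 − 0.025^(1/40) = 8.8%.
- With 3 lesions in 30, the exact 95% interval is 2.1% to 26.5%.
- Chance of seeing none in 30 at a true rate p: (1 − p)^30. The documents give no rate, so these are assumed values: 2% gives 0.98^30 = 55%, 5% gives 0.95^30 = 21%, and 10% gives 0.90^30 = 4%.

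An arm of this size can support a descriptive rate with an interval. It cannot support an unqualified statement that the device does not injure skin.

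**The case against.** The strongest reply is that recording AEs for oversight and follow-up is compatible with planning no statistical safety analysis. The same two-word entry also fills Sections 2.2, 2.3, 6.2 and 11.2.3, so in Sections 8 and 11.2.2 it may be a template entry meaning only that no dedicated safety tests are planned. The device is unpowered, contact skin is bandaged, and Section 5.2 excludes patients with active unhealed skin lesions. On this view the direct conflict is between Section 8 and Section 9.1, because collecting AEs is itself a safety assessment.

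Part of this stands. The clash with 11.2.2 is less direct than the clash with Section 8, and the safeguards are real. But a template entry still governs what the analyst does, and no other section overrides it.

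Three stronger readings are tempting, and the documents do not support them.

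- A reader might infer that this is the first use of the device in people. The documents call it novel, include prototype adjustment and give no earlier data, but they nowhere say first use.
- A reader might infer that the protocol expects skin injury. Section 2.4 words it as a possibility and gives a precaution.
- A reader might infer that AEs will never be reported. SAEs go to the IRB, all AEs are recorded and followed, and the general methods could be applied to them. What is missing is a pre-specified summary.

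It is also fair to say that the exact interval is good practice and not needed to remove the inconsistency, which counts and percentages would do. The figures above describe the precision of any arm of this size and do not measure the effect of the omission.

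**Conclusion.** The concern holds in this form: Sections 8 and 11.2.2 are inconsistent with Sections 2.4 and 9.1. Followed as written, they leave the trial with no planned safety summary beyond SAE reports to the IRB, so non-serious skin lesions would appear in no planned result. This is a stated rule that gives a worse report, not merely missing detail. It should be corrected, although no primary or secondary endpoint result changes.

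The finding itself rests only on the text. The illustration (upper limit 11.6% for 0 of 30, and a 21% chance of seeing none at a true rate of 5%) rests on 1:1 allocation, on all 30 device patients starting training, and on an assumed rate with no basis in the documents.

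**What to change.** Reconcile Sections 8 and 11.2.2 with 2.4 and 9.1.

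- **Section 8:** replace the entry with a reference to the AE recording in 9.1.
- **Section 11.2.2, safety set:** all randomised patients with at least one training session, analysed by treatment received. State that the complete-case rule in 11.4 does not apply to this set, nor the rule in 11.5 that leaves out data from patients who fail the inclusion criteria.
- **Tables by arm:** number and percentage with any AE, any SAE and any skin AE, by CTCAE grade and relatedness.
- **Device-arm patients only:** number and percentage with a device-related skin lesion, with an exact 95% interval. Identify these from the AE term and attribution already recorded. Controls do not use the device, so a between-arm comparison of device-contact lesions would have no meaning. Section 9.1 words attribution in terms of a study agent or drug, so say that here it means the device.
- **Non-patient device users:** list any recorded AEs separately. The plan does not spell out whether AE recording covers them.

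The cost is one or two tables from data already required. Sample size, visits and treatment are unchanged. One limitation should be stated with the result: no skin check is scheduled and 9.1 lists no body-site field, so the rate would rest on spontaneously recorded events and could be too low.
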